5 STATISTICAL ANALYSIS METHODS

5.1 General consideration

The statistical software, SAS[®], will be used for all summaries and statistical analyses.

This study only includes a single arm. In general, statistical analyses will be descriptive in nature with appropriate measures of variation provided where applicable. For continuous endpoints, number of subjects in the analysis population, number of subjects with non-missing observations, mean, standard deviation (SD), median, minimum and maximum will be reported. For categorical endpoints, number of subjects in the analysis population, number with non-missing observations, and the percent of those with data in each category will be summarized.

Several analysis populations are defined for different analysis purposes in this study. An overview of these analysis populations will be summarized.

- Pharmacodynamic Population - it is defined as all subjects who receive at least 1 dose of study treatment and have at least 1 pharmacodynamic measurement after Baseline.

CONFIDENTIAL

The information contained herein may not be used, disclosed, or published without the written consent of Biogen Idec MA Inc.

	Protocol 109MS310 An Open-Label Study to Assess the Effects of BG00012 on Lymphocyte Subsets in Subjects With RRMS	Final Version 1.0
---	---	--------------------------

- Safety Population – it is defined as all subjects who receive at least 1 dose of study treatment.

- [REDACTED]

[REDACTED]

In general, for data that are summarized by visit, any early withdrawal, unscheduled or scheduled visits will be assigned to an appropriate scheduled visit by using a mid-point of the two visits windowing scheme. The date of first dose will be the reference point. The detailed windowing rules for lymphocyte subsets, hematology, blood chemistry and vital signs are available in [Appendix 2](#). After windowing, if there is only 1 record in the visit window, then this record will be selected; if there are multiple records falling into the same visit window with different distance from the target day then select the one closest to the target day; if there are 2 visits with the same distance from the target day, but one is before the target day and the other is after the target day, then select the later one; for laboratory test, if more than one observation falls in the same distance from the target regular scheduled visit day, the mean observation will be calculated and used in the summary statistics and analyses.

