No imputation will be used for missing data in this study. The observed data will be used for all analyses.

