5.3.1 Analysis of the Primary Endpoint

The primary endpoints are the changes in lymphocyte subset counts for up to 48 weeks. The actual value, change and percent change from baseline in count and percent for each lymphocyte subset will be descriptively summarized at each applicable visit. Graphical display of median (Q1-25 percentile/Q3-75 percentile) of actual value and percent change from baseline in count and percent for each lymphocyte subset over time will also be presented. The Wilcoxon signed rank test will be used to test if the change and percent change from baseline in count and percent for each lymphocyte subset is different from zero. Listings of lymphocyte subsets will also be presented.

Furthermore, the primary endpoints will be summarized in various ALC subgroups to evaluate the nature of change in each subset in relation to the change in ALC.

ALC subgroups of interest include (1) subjects who have all ALC values \geq LLN ($0.91 \times 10^9/L$) up to Week 48, and (2) subjects who have at least 1 ALC value $<$ LLN over 48 weeks. A mixed model for repeated measures (MMRM) will be used to estimate the difference between ALC subgroups at each post-baseline visit up to Week 48. The model will be fitted with the change from baseline in count up to Week 48 for each of the TBNK lymphocyte subset as the dependent variable and will include ALC subgroup (all ALC values

CONFIDENTIAL

The information contained herein may not be used, disclosed, or published without the written consent of Biogen Idec MA Inc.

	Protocol 109MS310 An Open-Label Study to Assess the Effects of BG00012 on Lymphocyte Subsets in Subjects With RRMS	Final Version 1.0
---	---	--------------------------

\geq LLN up to Week 48; at least 1 ALC value $<$ LLN over 48 weeks), visit, corresponding Baseline counts, age, gender, and ALC subgroup-by-visit interaction as fixed effects. An unstructured variance-covariance matrix structure will be used in the MMRM model. Least squares (LS) mean, standard error, LS mean difference, 2-sided 95% confidence intervals (CIs) and p-values will be reported. Before the MMRM analysis, appropriate transformation may be performed based on the distribution of each TBNK lymphocyte subset parameter. The same analysis may be applied to other subsets.

Additional subgroups based on ALC values over time are defined:

- 1) ALC $< 0.5 \times 10^9/L$ for ≥ 6 months (24 weeks);

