Appendix 1 – List of reportable lymphocyte subset parameters

Lab test name (LabCorp)	Lab test code (LabCorp)	Lab label	Subset type
%CD24hi/CD38hi [CD19+/CD3-]	BCSB03	Transitional B-cells (% of B cells)	B Cell Subsets
%CD24hi/CD38hi/CD10+ [19+/3-]	BCSB08	CD10+ Transitional B cells (% of B cells)	B Cell Subsets
%CD27++/CD38++ [CD19+/CD3-]	BCSB09	Plasmablasts (% of B cells)	B Cell Subsets
%CD27++/CD38++/CD10- [19+/3-]	BCSB10	Plasma Cells [CD10-] (% of B cells)	B Cell Subsets
%CD27++/CD38++/CD138+ [19+/3-]	BCSB12	CD138+ Plasma Cells (% of B cells)	B Cell Subsets
%CD27+/IgD+ [CD19+/CD3-]	BCSB07	IgD+ Memory B cells [non-class switched] (% of B cells)	B Cell Subsets
%CD27+/IgD- [CD19+/CD3-]	BCSB06	IgD- Memory B cells [class switched] (% of B cells)	B Cell Subsets
%CD27-/IgD+ [CD19+/CD3-]	BCSB05	Naïve B cells (% of B cells)	B Cell Subsets
Absolute 27++/38++/10-[19+/3-]	BCSB22	Plasma Cells [CD10-] (cells/mm3)	B Cell Subsets
Absolute CD24hi/CD38hi[19+/3-]	BCSB15	Transitional B-cells (cells/mm3)	B Cell Subsets
Absolute CD27++/38++[19+/3-]	BCSB21	Plasmablasts (cells/mm3)	B Cell Subsets
Absolute CD27+/IgD+ [CD19+/3-]	BCSB19	IgD+ Memory B cells [non-class switched] (cells/mm3)	B Cell Subsets
Absolute CD27+/IgD- [CD19+/3-]	BCSB18	IgD- Memory B cells [class switched] (cells/mm3)	B Cell Subsets
Absolute CD27-/IgD+ [CD19+/3-]	BCSB17	Naïve B cells (cells/mm3)	B Cell Subsets
Absolute24hi/38hi/10+[19+/3-]	BCSB20	CD10+ Transitional B cells (cells/mm3)	B Cell Subsets
Absolute27++/38++/138+[19+MNC]	BCSB24	CD138+ Plasma Cells (cells/mm3)	B Cell Subsets
%CD11a+ [CD11c++]	A4S96	CD11a+ (% of dendritic cells [CD11c++])	VLA-4/LFA-1 Expression
%CD11a+ [CD19+]	A4S82	CD11a+ (% of B cells)	VLA-4/LFA-1 Expression
%CD11a+ [CD3+]	A4S68	CD11a+ (% of T cells)	VLA-4/LFA-1 Expression
%CD11a+ [Lymphs]	A4S26	CD11a+ (% of lymphocytes)	VLA-4/LFA-1 Expression
%CD11a+ [MNC]	A4S12	CD11a+ (% of MNC)	VLA-4/LFA-1 Expression
%CD11a+ [Monos]	A4S40	CD11a+ (% of monocytes)	VLA-4/LFA-1 Expression

CONFIDENTIAL

The information contained herein may not be used, disclosed, or published without the written consent of Biogen Idec MA Inc.

biogen idec	Protocol 109MS310 An Open-Label Study to Assess the Effects of BG00012 on Lymphocyte Subsets in Subjects With RRMS	Final Version 1.0
--------------------	---	--------------------------

%CD11a+ [Neut]	A4S54	CD11a+ (% of neutrophils)	VLA-4/LFA-1 Expression
%CD49d+ (9F10) [CD11c++]	A4S95	CD49d+ (% of dendritic cells [CD11c++])	VLA-4/LFA-1 Expression

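### The SAP has no rule for percent change when the baseline count is 0; in subsets with many zero baselines the percent-change test can drift towards a false decrease

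*SAP*

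**What the plan says.** SAP 5.3.1 sets this output for the primary endpoint: "The actual value, change and percent change from baseline in count and percent for each lymphocyte subset will be descriptively summarized at each applicable visit". Percent change is also tested against zero: "The Wilcoxon signed rank test will be used to test if the change and percent change from baseline in count and percent" for each subset. The planned plots are medians with quartiles "of actual value and percent change from baseline in count and percent for each lymphocyte subset over time will also be presented"; absolute change is not plotted.

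Appendix 1 is the list of reportable subsets. It contains broad populations (T, B and NK cells) and narrow ones: plasmablasts, CD138+ plasma cells (the count is listed as "CD138+ Plasma Cells (cells/mm3"), activated Th17 cells and terminal effector regulatory T cells, each as a count and as a percent.

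On missing values, SAP 5.1 states: "No imputation will be used for missing data in this study. The observed data will be used for all analyses". Tables will give the "number of subjects with non-missing observations, mean, standard deviation (SD), median, minimum and maximum will be reported". Baseline is a single record, the one closest to the first dose date (SAP 5.1 and Appendix 2). Neither document has a rule for a baseline of 0, a detection limit, an offset or a minimum baseline for percent change.

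**The concern.** Percent change divides by the baseline. A subject with a baseline of 0 has a defined actual value and a defined absolute change, but no percent change. Under an observed-data rule that subject drops out of the percent-change table, plot and test, and only those.

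This loss is not random, because the baseline reading itself decides it. The subjects removed could only have stayed at 0 or risen. Those kept had a positive baseline, some of them by chance, and will tend to read lower at the next visit. In a subset with many zero baselines, the test of percent change could therefore report a decrease when nothing has changed. A log ratio does not avoid the problem, since the log of 0 is also undefined.

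**Working it through.** **Inputs.** Evaluable subjects at Week 48: 180 (SAP section 4, which inflates to 180 / (1 - 0.10) = 200 enrolled; this reproduces). Significance level for the signed-rank test: not stated, assumed 0.05 two-sided in line with the SAP's 95% intervals. Subset counts, reporting resolution and share of zeros: not in the documents, so ranges are used. The plan states no figure of its own on this point.

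**Exact case.** Let baseline and visit counts be independent Poisson with the same mean m in every subject, with no drug effect.
- Share dropped = exp(-m). For m = 1 this is 0.368, leaving 180 x 0.632 = 114 subjects. For m = 0.5 it is 0.607, leaving 71.
- Mean baseline among those kept = m / (1 - exp(-m)). For m = 1 this is 1 / 0.632 = 1.58, while the mean at the visit is still 1. The kept group therefore falls by 0.58 units with no effect.
- Among those kept, the share reading 0 at the visit is exp(-m). This exceeds one half when m < ln 2 = 0.693, so below that mean the median percent change is -100%. At m = 1 the median is -50%; 55% of the kept subjects fall and 18% rise.

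**Simulation with between-subject spread.** 180 subjects, no effect, 1,000 trials per setting, percent change computed only where baseline > 0.

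Model A: zeros come from counting few events (Poisson; log-normal subject means with log SD 0, 0.6 or 1.0).

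| Mean | Dropped | Median % change | False decrease |
|---|---|---|---|
| 0.25 | 78-81% | -100% | 99-100% |
| 0.5 | 61-68% | -100% | 97-100% |
| 1 | 37-51% | -50% | 79-85% |
| 2 | 13-33% | 0 to -17% | 1-33% |
| 5 | 1-14% | 0 | 0-2% |

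With gamma-distributed subject means (400 trials per setting), the false-decrease rate at a mean of 1 is 78%, 65% and 35% for a coefficient of variation of 0.5, 1 and 2.

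Model B: zeros come from rounding to whole cells (log-normal values; between-subject log SD 0.6 or 1.0, within-subject log SD 0.2 or 0.4). A low subject then tends to read 0 at both visits, so there is less regression to the mean.

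| Median cells | Dropped | Median % change | False decrease |
|---|---|---|---|
| 0.25 | 74-86% | 0 (-25% in one setting) | 41-98% |
| 0.5 | 50% | 0 | 24-88% |
| 1 | 14-26% | 0 | 2-3% |
| 2 | 1-10% | 0 | 0-1% |

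**Absolute change in all subjects.** In these two tables' settings the same test on absolute change rejects in 4% to 7% of trials, close to nominal.

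**Higher counts.** Once few baselines are 0, the percent-change test leans the other way: in Model A at a mean of 5, false increases occur in 3% to 51% of trials. That comes from the skewness of percent change, which is a separate matter from the loss of zero baselines.

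**The case against.** The strongest case against has four parts.

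- **No zeros are shown.** Appendix 1 gives labels, not counts or detection limits, and the SAP nowhere says that subjects with a zero baseline are dropped. This is correct. The dropping is an inference from an undefined ratio plus the observed-data rule, and whether it matters depends on data the documents do not contain.
- **The size depends on where zeros come from.** This also stands. At a typical level of 1, Model A gives a false decrease in most trials under most spreads, and Model B gives 2% to 3%. A large false fall in the plotted median is mainly a feature of Model A.
- **The main results do not rest on percent change.** The primary endpoint is change in counts. SAP 5.3.1 already summarises absolute change and applies the same test to it. The mixed model uses change in count and is committed only for TBNK subsets. Protocol 16.2.2 calls the analyses descriptive, and a reduced non-missing n would be visible. All of this limits the consequence. It does not remove it: a reduced n does not reveal that the loss depends on baseline, and for the narrow subsets the mixed model is optional.
- **Abandoning percent change after a single zero would be excessive.** Agreed. In the exact case with a mean of 5, about 180 x exp(-5) = 1.2 zeros are expected, and at least one occurs in 1 - exp(-1.2) = 70% of trials, although the selection is then trivial. A threshold is needed.

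A reader might go further and infer that the plan will report false falls in rare subsets, or that such falls would be taken as confirming the drug's expected effect. The documents do not support either. They show no zero counts. Protocol 5.3.2 reports falls in mean leukocyte and lymphocyte counts, but Protocol 5.4 says that the effect on lymphocyte subtypes is not yet known.

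**Conclusion.** The gap is real but narrow. As written, SAP 5.3.1 with SAP 5.1 excludes subjects from the percent-change outputs because of their baseline reading. Where many baselines are 0, this biases a specified test towards a decrease.

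The size is conditional. For a mean of 1 event or less, the false-decrease rate is about 78% to 100% under most spreads tried, and lower with very wide gamma spread. Under whole-cell rounding it is about 24% to 98% at a median of 0.5 cells or less, usually with a median percent change of 0, and 2% to 3% at a median of 1. At a mean of 5 the effect is negligible unless subjects differ very widely. These figures rest on the assumed count models, 180 subjects and a two-sided 0.05 test.

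The absolute-change summary and test, and the TBNK mixed model, are untouched. This is an inexpensive improvement to secondary outputs for rare subsets. It does not call the primary analysis into question.

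**What to change.** Add to SAP 5.3.1:

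1. Report the number of zero baselines for each count and percent parameter.
2. Where zero baselines exceed a small pre-specified share of subjects (for example 5%, which is 9 of 180), do not test or plot subject-level percent change for that parameter.
3. For those parameters, base inference on absolute change in all subjects with both values, which is already planned, and plot it.
4. Replace subject-level percent change with a group-level figure, 100 x (mean at visit / mean at Baseline - 1), in those same subjects, with a bootstrap confidence interval.

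The cost is a few lines of SAP text and some programming. The drawback is that a few rare subsets will show a different percent-change measure from the rest, which a table footnote can explain. If no parameter crosses the threshold, the only addition is the count of zero baselines.

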Appendix 2 – Visit windowing rules

For Blood Chemistry, window to scheduled visits using the following windows:

Visit Name	Target Day	Study Day in Range Window
Baseline	first dose date	<= first dose date
Week 4	Day 29	(first dose date+1) to Day 42
Week 8	Day 57	Day 43 to Day 112
Week 24	Day 169	Day 113 to Day 252
Week 48	Day 337	Day 253 to Day 504
Week 96	Day 673	>=Day 505

For Hematology parameters, window to scheduled visits using the following windows:

Visit Name	Target Day	Study Day in Range Window
Baseline	first dose date	<= first dose date
Week 4	Day 29	(first dose date+1) to Day 42
Week 8	Day 57	Day 43 to Day 70
Week 12	Day 85	Day 71 to Day 126
Week 24	Day 169	Day 127 to Day 210
Week 36	Day 253	Day 211 to Day 294
Week 48	Day 337	Day 295 to Day 378
Week 60	Day 421	Day 379 to Day 462
Week 72	Day 505	Day 463 to Day 546
Week 84	Day 589	Day 547 to Day 630
Week 96	Day 673	>=Day 631

CONFIDENTIAL

The information contained herein may not be used, disclosed, or published without the written consent of Biogen Idec MA Inc.

biogen idec	Protocol 109MS310 An Open-Label Study to Assess the Effects of BG00012 on Lymphocyte Subsets in Subjects With RRMS	Final Version 1.0
--------------------	---	--------------------------

For the lymphocyte subsets, IgS and vital signs, window to scheduled visits using the following windows:

Visit Name	Target Day	Study Day in Range Window
Baseline	first dose date	<= first dose date
Week 4	Day 29	(first dose date+1) to Day 42
Week 8	Day 57	Day 43 to Day 70
Week 12	Day 85	Day 71 to Day 126
Week 24	Day 169	Day 127 to Day 210
Week 36	Day 253	Day 211 to Day 294
Week 48	Day 337	Day 295 to Day 420
Week 72	Day 505	Day 421 to Day 588
Week 96	Day 673	>=Day 589

For the physical exam (weight and height), window to scheduled visits using the following windows:

[figure not shown]
Visit Name	Target Day	Study Day in Range Window
Baseline	first dose date	<= first dose date
Week 48	Day 337	(first dose date+1) to Day 504
Week 96	Day 673	>=Day 505

CONFIDENTIAL

The information contained herein may not be used, disclosed, or published without the written consent of Biogen Idec MA Inc.

For the lymphocyte subsets in the lymphocyte follow-up period, window to scheduled visits using the following windows:

Visit Name	Target Day	Study Day in Range Window
Lymphocyte FU Baseline	lymphocyte follow-up start date	<= lymphocyte follow-up start date
4 weeks from Lymphocyte FU baseline	Day 29	Day 2 to Day 42
8 weeks from Lymphocyte FU baseline	Day 57	Day 43 to Day 70
12 weeks from Lymphocyte FU baseline	Day 85	Day 71 to Day 98
16 weeks from Lymphocyte FU baseline	Day 113	Day 99 to Day 126
20 weeks from Lymphocyte FU baseline	Day 141	Day 127 to Day 154
24 weeks from Lymphocyte FU baseline	Day 169	Day 155 to Day 210
36 weeks from Lymphocyte FU baseline	Day 253	Day 211 to Day 294
48 weeks from Lymphocyte FU baseline	Day 337	>= Day 295

CONFIDENTIAL

The information contained herein may not be used, disclosed, or published without the written consent of
Biogen Idec MA Inc.
